## 2. Statistical Method Description

2.1 Enrollment Analysis: List the number of enrolled and completed cases, and determine the analysis data sets (PPS, SS).

2.2 Demographic and Baseline Analysis: Descriptive statistics for demographic data and other baseline characteristics: Continuous variables: Calculate the number, mean, standard deviation, median, minimum, and maximum values. Categorical and ordinal data: Calculate frequencies and proportions. Inferential statistical results (P-values) will be listed as descriptive results. Age factors should be considered in data analysis, and data should be stratified or grouped by different age groups.

2.3 Efficacy Analysis: Primary Efficacy Indicators: Evaluate treatment effects through multi-omics analysis and platelet function indicators. Use descriptive and inferential statistical methods such as t-tests, chi-square tests, and Cox regression analysis to compare pre- and post-treatment differences. Secondary Efficacy Indicators: Include safety indicators and adverse event records. Use descriptive statistical methods such as frequency analysis and percentage calculations to describe the incidence and severity of adverse events.

	
2.4 Safety Analysis: Number and rate of laboratory indicators or physical examination abnormalities after treatment. List abnormal laboratory indicators, abnormal physical examination cases, and clinical interpretations.
 
2.5 Laboratory Data: Analyze changes in laboratory test results before and after treatment using paired t-tests or Wilcoxon signed-rank tests.
 
2.6 Adverse Events: Describe the types, frequencies, and severities of adverse events using chi-square tests or Fisher's exact tests for comparisons.
 
2.7 Multiple Comparison Adjustments: For multivariable statistical analyses, use Bonferroni correction or Holm-Bonferroni method to adjust significance levels and control type I error rates.
 
2.8 Critical Assumption Verification: Certain statistical methods require critical assumptions such as normality and homogeneity of variance. Verification methods include: Normality Test: Shapiro-Wilk test or Kolmogorov-Smirnov test. Homogeneity of Variance Test: Levene's test or Bartlett's test. This statistical analysis plan ensures the scientific rigor and reliability of data analysis. All statistical analyses will be performed using SAS or R software by professional statisticians

--	--

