## Clinical Research Protocol

Title	Clinical Study and Molecular Mechanism of Xuesaitong Soft Capsule in the Treatment of Acute Coronary Syndrome After Percutaneous Coronary Intervention
Version Number	2024XLA098-2
Responsible Institution	Xiyuan Hospital of China Academy of Chinese Medical Sciences
Target Population	Patients with Acute Coronary Syndrome (ACS) after Percutaneous Target Population Coronary Intervention (PCI), both male and female, aged between 18 and 80 years.
Objective	To interpret the microcosmic manifestations of ACS development using multi-omics technologies, explore key biomarkers and the correlation Objective between disease and syndrome, and elucidate the macro and microcosmic manifestations and biological basis of Xuesaitong soft capsule in the treatment of ACS from multiple perspectives.
Study Design	Single-center, open-label, exploratory clinical study.
Sample Size	50 ACS patients post-PCI in an open-label group.
Study Duration	From October 13, 2024, to December 1, 2026.
Inclusion Criteria	
(1) Patients diagnosed with acute ST-segment elevation myocardial infarction, acute non-ST-segment elevation myocardial infarction, or unstable angina according to Western medical standards. Inclusion Criteria.
 
(2) Within 4 weeks post-PCI.
 
(3) Aged between 18 and 80 years, both male and female.
 
(4) Voluntarily participating in the clinical trial, having signed the informed consent form.

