Exclusion Criteria	
 
(1) Uncontrolled hypertension after medication (systolic BP > 180mmHg or diastolic BP > 110mmHg).
 
(2) Increased bleeding risk: history of hemorrhagic stroke; intracranial aneurysm; major trauma or surgery within the past month (including Exclusion Criteria bypass surgery); active bleeding disorders.
 
(3) History of gastrointestinal ulcers or significant gastrointestinal bleeding.
 
(4) Severe organic heart disease, such as LVEF < 35% or NYHA/Killip heart function grade IV.
 
(5) History of malignant arrhythmias within the past year (arrhythmias affecting hemodynamics requiring medication or electrical cardioversion, or requiring CPR), congenital heart disease, or malignant tumors.
 
(6) Severe liver or kidney dysfunction: ALT or AST <math>\geq 3 \times \text{ULN}</math>, TBIL <math>\geq 2 \times \text{ULN}</math>, or creatinine clearance <math>< 30 \text{ ml/min}</math>.
 
(7) Pregnant or lactating women.
 
(8) Recent blood donation or significant blood loss within the past 3 months (<math>\geq 400 \text{ ml}</math>).
 
(9) History of alcohol abuse (<math>\geq 28</math> standard units/week for males, <math>\geq 21</math> standard units/week for females) or frequent alcohol consumption in the past 6 months (<math>\geq 14</math> standard units/week).
 
(10) History of drug abuse or dependence within the past year. Participation in other clinical trials and taking trial drugs within the past 3 months.
 
(11) Allergy or intolerance to aspirin or P2Y12 receptor inhibitors.
 
(12) Allergy to any components of the trial drug.
 
(13) Other conditions deemed inappropriate for participation by the investigator.
 

--------------------	---

Medication Information	
Trial Drug: Xuesaitong Soft Capsule.
 
Main Component: Panax Notoginseng Saponins.
 
Dosage Form: Capsule.
 
Dosage and Administration: Orally after meals, 0.33g per capsule, 2 capsules per dose, twice daily.
 
Storage Conditions: Room temperature, cool, dry place.

Medication Regimen	
Conventional Western medical treatment (oral medication and standard PCI) combined with Xuesaitong soft capsule, 0.33g per capsule, 2 capsules per dose, twice daily for 4 weeks.

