Study Procedure	
Participants who meet the diagnostic criteria, inclusion, and exclusion criteria, and have signed the informed consent form will be included in the study. The open-label study period is 4 weeks, including 2 visits: Visit 1 (-1D to 0D) and Visit 2 (4w ± 3d), with no follow-up period.

Evaluation Criteria	
(1) General Information: Demographic data, physical examination, medical history, allergy history, smoking and alcohol history, concomitant medications.
 
(2) Multi-omics Analysis: Including platelet transcriptomics, metabolomics, proteomics, microbiomics.
 
(3) Platelet Function: platelet granule markers (PF4 and <math>\beta</math>-TG), surface activation markers (P-selectin/CD62P, GPIIb/IIIa complex/CD41/CD61), platelet-leukocyte aggregation (CD41 and CD15).
 
(4) Safety Indicators: Routine blood, urine, and stool tests (including occult blood), liver and kidney function tests, ECG, coagulation function, and adverse event recording.

Statistical Analysis Plan	
1. Analysis Data Sets
 
1.1 Full Analysis Set (FAS): Defined according to the ITT principle, including all enrolled participants who received at least one treatment.

1.2 Per-Protocol Set (PPS): Includes participants who met inclusion criteria, completed treatment and follow-up, had medication compliance between 80-120%, did not use concomitant medications affecting efficacy evaluation, had complete main outcome data, and no major protocol violations.

1.3 Safety Set (SS): Includes all enrolled participants who received at least one treatment. Baseline data analysis will be conducted separately for FAS and PPS. Efficacy indicators will be analyzed for both FAS and PPS. Safety and adverse events will be analyzed for SS.

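### Section 2.3 treats one-arm pre/post changes as treatment effects, but they mix any Xuesaitong effect with post-PCI recovery and conventional treatment, so they cannot support the Xuesaitong part of the objective

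*Combined protocol and SAP*

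**What the plan says.** All references are to the combined protocol and SAP.

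- **Study Design and Sample Size:** "Single-center, open-label, exploratory clinical study", with "50 ACS patients post-PCI in an open-label group". No comparator is described.
- **Inclusion Criteria:** item "2) Within 4 weeks post-PCI".
- **Medication Regimen:** "Conventional Western medical treatment (oral medication and standard PCI) combined with Xuesaitong soft capsule", for 4 weeks, for everyone.
- **Study Procedure:** two visits only, "Visit 1 (-1D to 0D) and Visit 2 (4w ± 3d), with no follow-up period".
- **Objective:** three strands, namely the development of ACS, biomarkers and the link between disease and syndrome, and the "biological basis of Xuesaitong soft capsule in the treatment of ACS from multiple perspectives". Only the third is about the drug.
- **Statistical plan, 2.3:** "Primary Efficacy Indicators: Evaluate treatment effects through multi-omics analysis and platelet function indicators", using descriptive and inferential methods to compare values before and after treatment.
- **Statistical plan, 1.2 and 1.3:** efficacy is analysed in both FAS and PPS. The PPS is limited to patients who, among other conditions, "did not use concomitant medications affecting efficacy evaluation".

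The documents contain no concurrent or historical control, run-in, repeated baseline, rule on stable background medication, adjustment for time since PCI, or statement limiting how the change may be interpreted.

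**The concern.** A within-patient change estimates a treatment effect only if the marker would otherwise have stayed where it was. That is hard to assume here. Patients are recruited in the weeks after an acute coronary event and a PCI, and all of them take conventional treatment over the same 4 weeks. The exclusion for allergy or intolerance to aspirin or P2Y12 inhibitors suggests that this background includes antiplatelet drugs, although the documents do not list it. Platelet activation markers are among the primary indicators, so the mixing bears directly on the endpoint.

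The interpretation of the primary analysis is at stake. Under 2.3, a shift in an omics or platelet marker can be reported as a treatment effect and carried into a statement about how Xuesaitong works. The design supports a narrower statement: what changed while patients took Xuesaitong plus standard care.

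**Working it through.** **The plan's own figure.** The sample size of 50 is given without alpha, power, effect size or SD, so it cannot be reproduced. It is not in dispute.

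**What the change contains.** For any marker, in units of the SD of the change score, write

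mean change = D + R + C

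where D is the Xuesaitong effect, R is recovery after ACS and PCI (with any regression to the mean), and C is the effect of conventional treatment between the visits. One group and two time points yield one mean change per marker, so D is not identified. For example, with B = R + C, the pairs (D, B) = (0.3, 0), (0, 0.3) and (-0.2, 0.5) all give a mean change of 0.3 SD and the same chance of significance.

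**Does any existing text remove the mixing?**

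| Text | What it does | Removes R or C? |
|---|---|---|
| Exploratory label (Study Design) | Describes the study | No; 2.3 still applies inferential tests to treatment effects |
| P-values listed as descriptive (2.2) | Covers demographic and baseline data | No; it is not in 2.3 |
| Bonferroni or Holm (2.7) | Controls chance findings | No; a real background change is not a chance finding |
| PPS medication rule (1.2) | Excludes some patients | No; recovery and the shared regimen remain, and FAS is analysed too |

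**Illustration of size.** From the documents: n = 50. Assumed: paired t-test (2.3 says only t-tests; the paired test is named in 2.5), two-sided 0.05, 50 complete pairs, no multiplicity adjustment, D = 0, and background change B of 0.2, 0.3 or 0.5 SD.

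1. Significance threshold: t(0.975, 49)/√50 = 2.010/7.071 = 0.284 SD. An observed mean change larger than this gives p<0.05 whatever its cause.
2. Chance of p<0.05: the non-central t distribution with 49 degrees of freedom and non-centrality B√50.

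| B (SD) | Non-centrality | Chance of p<0.05 per marker |
|---|---|---|
| 0.2 | 1.41 | 28% |
| 0.3 | 2.12 | 55% |
| 0.5 | 3.54 | 93% |

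3. With multiplicity adjustment at B = 0.3 (test counts assumed): 30% at 0.05/5 = 0.01, and 1.8% at 0.05/1000. Adjustment lowers the rate but leaves the bias in the estimate unchanged.
4. With 40 complete pairs (an assumed PPS): the threshold is 2.023/√40 = 0.320 SD, and the three rates are 23%, 46% and 87%.
5. A larger sample does not help: at B = 0.3 and unadjusted 0.05, the rate is 84% with n = 100 and 99% with n = 200.

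**The case against.** The strongest reply is that 2.3 never names Xuesaitong. The Medication Regimen defines treatment as the combination, so a treatment effect can fairly mean the effect of the combined regimen. That reading is open, and on it C is no longer a contaminant in 2.3. Recovery still is, and the objective still asks about Xuesaitong specifically.

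A second reply is that an exploratory single-group study is a legitimate way to describe change and generate hypotheses. That stands. A reader might infer that the design is invalid, or that a control arm is required. The documents do not support this: what needs correcting is the label on the estimate.

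A third reply concerns the percentages. They depend on background changes that the documents do not supply, and on an alpha and a paired test that 2.3 does not state. The 55% figure is also unadjusted although 2.7 plans adjustment, and at omics-scale test counts it falls to about 2%. All of this is right. The figures show how the mechanism works and do not estimate this trial's error rate. The identification argument does not need them.

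A reader might also infer that the plan declares success on a significant p-value. It does not: no alpha, success rule or decision is tied to significance.

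**Conclusion.** The concern holds in a limited form. The pre/post changes in 2.3 cannot support the Xuesaitong part of the objective, because the design has no element that separates the drug from recovery and conventional treatment, and no text states that limit. This follows from the design alone.

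It would go too far to infer that the whole objective fails. The strands on ACS development and on biomarkers and syndrome do not need attribution to the drug.

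The practical size is unknown because the documents give no background change. Under the assumptions above, 0.2 to 0.5 SD would produce nominal significance in 28% to 93% of trials per marker with no drug effect, and far less often under strict adjustment. This should be fixed: it concerns the primary analysis, but wording alone corrects it.

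**What to change.** 1. In 2.3, for both the multi-omics and the platelet indicators, replace the treatment-effects wording with: *estimate the change from baseline during 4 weeks of Xuesaitong plus standard care*.
2. Add to 2.3: *These changes and their P-values, in FAS and PPS alike, cannot be attributed to Xuesaitong alone and are hypothesis-generating.*
3. Align the Xuesaitong strand of the Objective with that wording, so that it describes changes seen during combined treatment. Leave the other strands as they are.

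No new patients, visits, data or tests are needed, and treatment does not change. The cost is a more modest claim about the drug.

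A concurrent control on the same conventional treatment would address attribution, but it is a different study and is not needed for this correction. For scale, splitting 50 patients 25:25 would detect, with 80% power at two-sided 0.05 (both assumed), a difference in change of √(2/25) × (1.96 + 0.84) = 0.79 SD. Adjusting the one-arm change for time since PCI would help describe it but would not isolate the drug.

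### Section 2.3 calls uncontrolled before-after marker changes primary efficacy; no listed outcome is assigned to the 'macro' aim, and no patient-level count of ischaemic events is separated out

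*Combined protocol and SAP*

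**What the plan says.** The Study Design row describes a "Single-center, open-label, exploratory clinical study", and the Sample Size row gives "50 ACS patients post-PCI in an open-label group". The drug is added to standard medication and PCI care for four weeks (Medication Regimen). There are two visits, at baseline and at week 4, and nothing afterwards (Study Procedure).

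The Objective row includes the aim to "elucidate the macro and microcosmic manifestations and biological basis of Xuesaitong soft capsule in the treatment of ACS from multiple perspectives". It does not define 'macro'.

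Section 2.3 sets the main outcome: "Primary Efficacy Indicators: Evaluate treatment effects through multi-omics analysis and platelet function indicators". The Evaluation Criteria row spells out the omics part ("Including platelet transcriptomics, metabolomics, proteomics, microbiomics") and the platelet part, which consists of granule markers, surface activation markers and platelet-leukocyte aggregation.

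Section 2.3 then makes safety indicators and adverse event records the secondary efficacy indicators, with incidence and severity summarised by frequencies and percentages. The safety domain of the Evaluation Criteria ends with "ECG, coagulation function, and adverse event recording". Section 2.6 says: "Describe the types, frequencies, and severities of adverse events".

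**The concern.** There are two linked problems.

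The first is the label. Section 2.3 presents before-after marker changes as efficacy and as effects of treatment. There is no control group, and patients enter within four weeks of PCI for an acute event while on conventional treatment. Markers may move in that period for reasons other than the study drug. A report that follows the plan's wording would present a favourable shift as efficacy.

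The second is the objective. It promises macro as well as microscopic manifestations in treating ACS, yet no symptom measure, syndrome score, ischaemic event or clinical composite is named as an outcome. Ischaemic events that are recorded as adverse events would enter the general adverse event summaries, but nothing says how many patients had one. A reader could see a favourable marker result without the accompanying clinical course in the same 50 patients.

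**Working it through.** **Inputs.** From the documents: n = 50, one group, four weeks, before-after comparison. The documents give no power calculation, marker variability or ischaemic event rate, so there is no figure of the plan's own to reproduce. Everything marked *assumed* below is illustrative.

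**1. What a before-after change estimates.** In a single group,

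mean change = drug effect + change from all other causes (recovery, background treatment, regression to the mean).

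There is one observed quantity and two unknowns, so the drug effect is not identified. To show the size, suppose the drug does nothing and other causes shift a marker by δ standard deviations of the paired differences (*assumed*). A paired t-test at two-sided 5% with 50 complete pairs has power P(|T| > t(0.975; 49)), where T is noncentral t with 49 degrees of freedom and noncentrality δ√50:

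| δ (assumed) | Chance of a significant change |
|---|---|
| 0.3 | 55% |
| 0.4 | 79% |
| 0.5 | 93% |

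This is for one marker before any correction under section 2.7. A correction would lower these chances but would not change what is being estimated.

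**2. Objective against outcomes.**

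| Evaluation domain | Role in the SAP | Assigned to 'macro'? |
|---|---|---|
| General information | Baseline description (2.2) | No |
| Multi-omics | Primary efficacy (2.3) | No; laboratory assays |
| Platelet function | Primary efficacy (2.3) | No; laboratory assays |
| Safety indicators, including ECG and adverse events | Secondary efficacy (2.3) and safety (2.4 to 2.6) | Not stated |

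Section 2.3 also lists Cox regression, but no time-to-event endpoint is defined for it.

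**3. What a patient-level ischaemic count would show.** Exact (Clopper-Pearson) 95% limits for x of 50 patients are the 2.5% quantile of Beta(x, 51 − x) and the 97.5% quantile of Beta(x + 1, 50 − x). For x = 0 the lower limit is 0 and the upper limit is 1 − 0.025^(1/50) = 7.1%.

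| Patients with an event | Rate | Exact 95% interval |
|---|---|---|
| 0 | 0% | 0 to 7.1% |
| 1 | 2% | 0.05 to 10.6% |
| 2 | 4% | 0.5 to 13.7% |
| 3 | 6% | 1.3 to 16.5% |

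The expected number is 50p, and the chance of no event is (1 − p)^50:

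| Four-week rate p (assumed) | Expected | Chance of none |
|---|---|---|
| 1% | 0.5 | 0.61 |
| 2% | 1.0 | 0.36 |
| 5% | 2.5 | 0.08 |
| 10% | 5.0 | 0.005 |

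**4. Why a listing by type does not give this count.** Section 2.6 does not say whether it counts patients or events. Suppose an infarction, a stent thrombosis and a revascularisation are recorded. If they occurred in one patient, the rate is 1/50 = 2% (0.05 to 10.6%). If they occurred in three patients, it is 3/50 = 6% (1.3 to 16.5%). Both cases can print as the same three rows.

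**The case against.** The strongest reply is that the study is exploratory, its title includes molecular mechanism, and its objective is mainly about omics, biomarkers and biological basis. Marker endpoints suit that aim, and nowhere do the documents say that a clinical efficacy conclusion will be drawn. This stands as a defence of the choice of assays. It does not defend the label in section 2.3, which is the wording a report would inherit.

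Three stronger readings are tempting, and the documents do not support them.

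- A reader might infer that ischaemic events are never counted, or that only markers carry the word efficacy. Section 2.3 makes adverse event records a secondary efficacy indicator with incidence described, so recorded events would be in that total. What is missing is a definition and a separate patient-level count.
- A reader might infer that these events are already captured. The documents list ECG and adverse event recording only. They do not say that recurrent ischaemia is recorded as an adverse event or how ECGs are read for it, and an ECG alone cannot show a readmission or whether a procedure was planned.
- A reader might equate 'macro' with ischaemic events. The objective does not define the word, and it also mentions the correlation between disease and syndrome, so symptoms or syndrome features are at least as plausible.

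It is also fair to say that a four-week count in 50 uncontrolled patients says little about efficacy. That is why the count should be descriptive only.

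**Conclusion.** The point holds as a modest one about labelling and reporting. It is not a fault in the choice of assays or in the sample size. Section 2.3 attaches efficacy and treatment effect to before-after marker changes that this single-arm design cannot attribute to the drug. The 'macro' part of the objective has no assigned outcome, although adverse events, ECG and physical examination findings are reported as safety data. No patient-level ischaemic count is separated out.

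The label problem follows from the design alone and needs no assumed number. The size of the event row assumes that all 50 patients are treated and enter the Safety Set. Even with no events, a rate of up to 7.1% remains compatible with the data, and with three patients the limit is 16.5%. Neither result could support or refute clinical efficacy. The value of the row is that it puts the clinical course beside the marker result. This matters because the per-protocol set requires completed treatment and complete main outcome data, and no missing-data rule is given for the full analysis set. Patients with events may therefore drop out of the marker comparison.

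**What to change.** 1. In section 2.3, rename the primary indicators *primary mechanistic (pharmacodynamic) indicators*, and add: *No conclusion on efficacy in treating ACS will be drawn from these indicators.*
2. Confirm that adverse event recording covers cardiac death, infarction, stent thrombosis, unplanned revascularisation and readmission for angina. Give a short definition of each, including how staged procedures are told apart from unplanned ones.
3. Add one descriptive row in the Safety Set: the number and percentage of patients with at least one such event recorded as an adverse event between Visit 1 and Visit 2, with an exact 95% interval and each patient counted once.
4. Either name the measure that answers the 'macro' aim or remove the word from the objective. The ischaemic row should carry that name only if the sponsor decides that this is what was meant.

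**Cost.** SAP wording and one table row, with no change to treatment, visits or sample size. If step 2 shows that the events are not covered, the row also needs an addition to adverse event recording. **Downside.** The claim becomes mechanistic, and the event interval will be wide.

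### Section 2.3 gives the primary multi-omics comparison a test list that does not fit it: no stated pairing, normalisation or transformation, and Cox regression without a time-to-event endpoint

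*Combined protocol and SAP*

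**What the plan says.** SAP section 2.3 defines the primary efficacy indicators in one line: "Evaluate treatment effects through multi-omics analysis and platelet function indicators". The Evaluation Criteria, item (2), list the omics layers: "Including platelet transcriptomics, metabolomics, proteomics, microbiomics". For all primary indicators together, section 2.3 then names "methods such as t-tests, chi-square tests, and Cox regression analysis to compare pre- and post-treatment differences".

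Three other sections bear on the point:

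- Section 2.5, for laboratory data only: "Analyze changes in laboratory test results before and after treatment using paired t-tests or Wilcoxon signed-rank tests".
- Section 2.7: "use Bonferroni correction or Holm-Bonferroni method to adjust significance levels and control type I error rates". Its opening words confine this to multivariable analyses, so it is unclear whether feature-by-feature tests are covered.
- Section 2.8: "Certain statistical methods require critical assumptions such as normality and homogeneity of variance". It offers tests of those two assumptions and no others.

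The sample is "50 ACS patients post-PCI in an open-label group", seen at baseline and at 4 weeks with no later follow-up. No section gives a normalisation, library-size adjustment, log or log-ratio transformation, count model or rule for zeros for any omics layer. The assay platforms and data scales are not stated either.

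**The concern.** The study's objective is to find biomarkers and explain mechanism, so its main product will be lists of features that changed between two visits. Those lists depend on choices that section 2.3 leaves open.

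The named methods are a poor guide to those choices. The design is one group measured twice, which calls for within-patient analysis. Microbiome results are commonly expressed as shares of a total. When one share rises the others must fall, so a test on shares can flag taxa whose absolute amount did not move. That shift is systematic. A multiplicity correction raises the bar but does not remove the cause, and the normality and variance checks in section 2.8 would not reveal it.

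**Working it through.** **Fit of the named methods to the design.** The plan gives no alpha, power, effect size or SD, so it has no figure of its own to reproduce here. The first check is a comparison of method with design.

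- *t-test:* section 2.3 does not say paired; section 2.5 does, but only for laboratory results. As an illustration, assume a between-patient log SD of 0.8 and a within-patient log SD of 0.5 per visit. The variance of a within-patient difference is 2 × 0.5² = 0.50. An unpaired analysis uses 2 × (0.8² + 0.5²) = 1.78, which is 1.78/0.50 = 3.6 times as large.
- *Chi-square:* the standard test assumes independent observations, which two visits of the same patient are not.
- *Cox regression:* with two fixed visits and no follow-up, none of the omics or platelet measures is a time to an event.

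**Effect of working with shares.** If a taxon with share s rises f-fold and nothing else changes, the total becomes 1 + s(f − 1). Every other share is then multiplied by 1/[1 + s(f − 1)]. With s = 0.30 (assumed):

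- f = 1.5: 1/1.15 = 0.870, a fall of 13%
- f = 2: 1/1.30 = 0.769, a fall of 23%
- f = 3: 1/1.60 = 0.625, a fall of 37.5%

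**Simulation.** Only the 50 pairs come from the plan. Assumed: 100 taxa, log-normal abundances with the SDs above, 20,000 reads per sample, one dominant taxon changing and 99 unchanged; 150 replicates per setting (30 for Wilcoxon). The entries are the percentage of unchanged taxa with unadjusted P<0.05.

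| Share, rise | Paired t, raw shares | Paired t, log shares | Wilcoxon, raw shares | Paired t, CLR |
|---|---|---|---|---|
| 30%, none | 4.1 | 5.1 | 5.4 | 5.3 |
| 10%, 2-fold | 8.4 | 12.8 | 10.6 | 5.1 |
| 30%, 1.5-fold | 10.1 | 17.2 | 15.8 | 5.3 |
| 30%, 2-fold | 24.3 | 46.2 | 33.8 | 5.2 |
| 30%, 3-fold | 60.0 | 89.8 | 81.7 | 5.2 |

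Repeat runs of the raw-share test gave 9.9% to 10.8%, 24.0% to 25.1% and 59% to 60.1% for the three rises at a 30% share. A log without a reference makes matters worse, because it detects the fall in share more efficiently. Borrowing the rank test from section 2.5 does not help.

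**With Bonferroni.** The threshold is 0.05/100 = 0.0005. Mean false taxa per trial for 1.5-, 2- and 3-fold rises at a 30% share:

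- raw shares: 0.11, 0.63 and 5.6 (repeat runs: 0.09 to 0.10, about 0.6, and 6.2 to 7.3)
- log shares: 0.68, 4.4 and 34.6
- CLR: 0.03, 0.06 and 0.03

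As a fraction of the 99 unchanged taxa, the raw-share figure for a 2-fold rise is 0.63/99 = 0.6%.

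**Limits of CLR.** CLR divides by the geometric mean of all taxa. If k of 100 taxa double, that mean rises by 2^(k/100), and each unchanged taxon appears to move by the inverse:

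- k = 1: 2^(−0.01) = 0.993, a fall of 0.7%
- k = 20: 2^(−0.20) = 0.871, a fall of 13%
- k = 30: 2^(−0.30) = 0.812, a fall of 19%

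Simulation agrees. With 20 taxa doubling, 25.6% of unchanged taxa were flagged on raw shares and 24.8% on CLR; with 30 doubling, 45.6% and 48.2%. After Bonferroni in the 30-taxon case, CLR left 3.7 false taxa per trial and raw shares 1.9.

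**The case against.** The best defence is that section 2.3 offers its tests as examples. The list also has to serve the platelet function markers, for which a t-test on within-patient change is reasonable. Nothing says that t-tests will be run on raw counts or untransformed shares, and a paired t-test on log-ratio data is still a t-test. This stands. A reader might infer that following section 2.3 necessarily puts false features on the lists, or that the three named methods themselves create them. The documents do not support either reading: any artefact comes from the scale on which the data are tested, and that scale is not stated. The simulation also says nothing about chi-square or Cox, where the objection is fit to the design.

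Three further points stand. The unadjusted percentages would overstate the effect if section 2.7 is applied feature by feature. The scenarios are assumed, since the documents do not suggest that one taxon holds 30% of the community or doubles in 4 weeks. And a taxon whose share falls has truly changed in relative abundance; calling it unchanged presumes an absolute target that the plan never names.

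What the defence does not answer is that the examples are the only guidance for the primary omics data. Two of the three do not suit a paired, two-visit comparison, and the choices that decide the result are left until the data are in hand.

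**Conclusion.** The point holds as a gap in specification that should be closed. Section 2.3 does not state pairing, normalisation or scale for its primary omics data, and it names Cox regression and chi-square without an endpoint or design that suits them. That part rests on the documents alone.

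The numerical part is conditional. If t-tests were run on raw shares and a taxon holding 30% rose 1.5-, 2- or 3-fold, about 10%, 25% or 60% of unchanged taxa would reach unadjusted P<0.05. Bonferroni would leave about 0.1, 0.6 or 6 per trial. The problem is therefore material mainly for large shifts and absent when nothing dominant moves. The simulation covers microbiome-type data only. That transcript data arrive as counts is an inference, and nothing was computed for transcriptomics, metabolomics or proteomics. It would also be wrong to conclude that CLR guarantees the nominal error rate, since it gives no protection when many taxa change together. As the study is exploratory, the gap weakens the reading of its feature lists; it does not invalidate the design.

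**What to change.** In section 2.3, separate the omics data from the platelet function markers and replace the test list for omics with within-patient methods by layer:

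- **Microbiome:** a prevalence filter and a paired analysis on a log-ratio scale, with a second reference or normalisation as a sensitivity check. State that results concern relative abundance unless absolute quantity is measured.
- **Transcriptomics:** a library-size-normalised count model, or a precision-weighted linear model, with patient as a blocking factor.
- **Metabolomics and proteomics:** paired differences on the log scale, with the normalisation stated.

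Drop Cox regression and unpaired chi-square for these data. Control the false discovery rate within each layer, which suits exploratory feature discovery, and say how section 2.7 then applies. False discovery rate control does not remove a systematic shift either, so this change should go in together with the choice of scale.

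The cost is a few lines of SAP text and standard code in R, which the plan already allows. No extra patients, samples or visits are needed. The downsides are slightly more analysis work, effects reported on a log or log-ratio scale, and looser error control than Bonferroni or Holm.
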